6.1 Documentation

This is a registry study observing on-label use of HydroPearl microspheres; therefore, all product will be obtained from the commercial stock at each study site for clinical use. All product information should be recorded in source documents and the study eCRF.

6.2 Malfunctioning / Failed Device

If a Terumo device has malfunctioned and/or failed, the investigator must follow the standard institutional policies for reporting complaints. In addition, the device failure should be reported in the eCRF.

7 General Procedures

7.1 Screening/ Baseline Visit

Prior to the procedure, subjects must sign the informed consent form, meet all the inclusion and none of the exclusion criteria. The screening visit will follow each study site's standard of care and typically consists of a review of medical history and demographics, blood tests, imaging, review of concomitant medications, and pregnancy test if appropriate.

7.2 Procedure

Subjects that meet the eligibility criteria and have signed the informed consent will have their scheduled procedure performed in accordance with investigator/site standard practices. Any on-label use of HydroPearl microspheres are permitted this study; that is, treatment of arteriovenous malformations and hypervascular tumors including uterine fibroids.

Table 2: Schedule of Events

Assessment	Screening / Baseline	Procedure	Discharge	30 Day Follow-up ±14 days	180 Day Follow-up ±30 days	365 Day Follow-up ±30 days
Informed Consent	X					
Eligibility Criteria	X					
Medical History/Demographics	X					
Pregnancy Test [¶]	X					
Blood Tests, including platelets and INR (if available) *	X	X	X	X	X	X
Embolized target organ Imaging (if available)	X	X	X	X	X	X
Physical Exam	X	X	X	X	X	X
Procedure, Access, Closure Evaluations		X				
Quality of Life questionnaires and return to normal activities	X		X	X	X	X
Concomitant Medications (Intra-op and Anticoagulation / Antiplatelets Only)	X	X	X	X		
Device Related Adverse Events ^{§§}		X	X	X	X	X

[¶] Pregnancy test if female of child-bearing potential (collected prior to procedure according to site standard of care)

* Blood Tests include Complete Blood Count (CBC), Platelet Count, Serum Creatinine, Hemoglobin (HGB), Blood Urea Nitrogen (BUN), Hematocrit (HCT) and Prothrombin time/INR, only as collected per standard of care

^{§§} Device related adverse events should be recorded during the entire course of the study from time of enrollment through end of 180 Day Follow-up visit.

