2.2 Sample Size

Up to 10 sites in the US and EU are expected to participate in the study with 100 subjects enrolled. Each study site will be limited to 30% of total patient population.

The target population is comprised of subjects scheduled for embolization procedures with HydroPearl microspheres used on-label via radial access.

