3.2.2 Additional Evaluations

Additional evaluations include:

1. Incidence of Radial Artery Occlusion Complications at any time
 - a. Arteritis
 - b. Cellulitis
 - c. Ecchymosis
 - d. Pain at puncture site
 - e. Hematoma

2. Quality of Life and health economics
3. Post embolization syndrome
4. Procedural endpoints:
 - a. Blood loss
 - b. Patient radiation exposure
 - c. Contrast volume
 - d. Time to hemostasis
 - e. Total procedural time
 - f. Time to discharge
 - g. Operative time
5. Access endpoints:
 - a. Radial artery spasm,
 - b. Time to discharge
6. Closure endpoints
 - a. Time to hemostasis
 - b. Time to ambulation
7. Tumor type
8. Number and size of tumors / fibroids
9. Post embolization syndrome
10. UFE:
 - a. If post-op MRI is obtained per standard of care: Effectiveness of HydroPearl measured by MRI.
 - i. Infarction is characterized by complete (100%), 90-99%, 50-89%, or less than 50%.
 - ii. Uterine Volume
 - iii. Dominant Fibroid Volume
 - b. EQ-5D
 - c. UFS-QoL
 - d. Return to normal activities
 - e. Pain VAS
 - f. Symptoms including bleeding and bulk
 - g. Pregnancy intention and occurrence
11. PAE:
 - a. IPSS with Quality of Life

- b. EQ-5D
- c. Return to normal activities
- d. Pain VAS
- e. Qmax
- f. Prostate volume

12. Liver Tumor Embolization:

- a. Tumor response (mRECIST - CR, PR, SD, PD)
- b. EQ-5D
- c. Return to normal activities
- d. Pain VAS
- e. Disease stage

13. Other Hypervascular Tumors

- a. Infarction
- b. Tumor Response (mRECIST – CR, PR, SD, PD)
- c. Return to normal activities
- d. Pain VAS

14. Arteriovenous malformations:

- a. EQ-5D
- b. Return to normal activities
- c. Pain VAS

4 Study Design

This is a prospective, multi-center, registry study to assess the procedural success, technical success, and complication rate of radial access procedures using HydroPearl microspheres.

A subject is considered enrolled into the study once the guidewire is inserted into the radial artery.

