7.6.1 Discharge Visit

The subject may be discharged when clinically stable, at the discretion of the investigator.

7.6.2 30 Day Visit (\pm 14 days)

All study sites will be asked to collect follow-up data per each subject at 30 days post-procedure. Study reported evaluations are not required except for the quality of life questionnaire; otherwise all data collected will be per standard of care. A typical follow-up visit may include blood tests, imaging, physical exam, review of concomitant medications and any device related adverse events.

7.6.3 180 Day Visit (\pm 30 days)

All study sites will be asked to collect follow-up data for each subject at 180 days post-procedure, per site standard of care. Study reported evaluations are not required except for the quality of life questionnaire; otherwise all data collected will be per standard of care. A typical follow-up visit may include blood tests, imaging, physical exam, review of concomitant medications and any device related adverse events.

7.6.4 365 Day Visit (\pm 60 days)

All study sites will be asked to collect follow-up data via telephone or visit for each subject at 365 days post-procedure. If a clinic visit is standard of care at 365 days, data from the visit will be collected. If a clinic visit is not standard of care, follow-up information for this visit will be collected via telephone. This 365-day visit will conclude the subject's participation in the study.

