7.7 Clinical Data Collection

Information about subject demographics, eligibility requirements, procedure, specific concomitant medications as well as complications and/or device related adverse events will be collected on the eCRFs provided by the Sponsor. The eCRFs should accurately reflect data contained in the subject's medical records (i.e. source documents).

8 Adverse Events

Subject complications will be monitored via the reporting of device related adverse events occurring from the time of enrollment (insertion of guidewire into radial artery) through study completion (withdrawal for any reason or completion of 365-day follow-up visit). For this registry, adverse events collected will be limited to any events possibly, probably or definitely related to a Terumo device, as described below in Section 8.2.

Where an adverse event has, by its nature, a prolonged course, the event will be considered a single event and not multiple events.

The investigator is not required to actively seek adverse events from a subject once a subject has exited the study. If the investigator learns of any device related adverse event at

any time after a subject's exit from the study, the investigator should promptly report it to the Sponsor.

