8.3 Follow-up of Adverse Events

All device related adverse events observed from the time of enrollment throughout the duration of the study must be reported on the eCRF. All device related adverse events will be followed until resolution or stabilization of symptoms through study completion and/or the subject withdraws consent. Resolution means that the subject has returned to a baseline state of health. Stabilization means that the investigator does not expect any further improvement or worsening of the adverse event.

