13.2.1 Study Visit

The Study Visit Day 0 is the date of the index procedure. Day in study will be calculated relative to the index procedure as follows:

$$\text{Study Day} = \text{Assessment Date} - \text{Index Procedure Date}$$

For each subject, duration in study will be based on last study contact date which is the latest date of all follow-up visits, assessments, adverse event onset or resolution, and study exit including date of death.

Duration variables will be calculated as follows:

$$\text{Duration Days} = \text{End Date} - \text{Start Date}$$

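### Table 2's footnote stops device-related adverse event recording at the 180-day visit, while the rest of the protocol carries it to 365 days; the 365-day window is also given as both ±30 and ±60 days

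*Combined protocol and SAP*

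**What the plan says.** **Recording period.** The Table 2 footnote attached to the device-related adverse event row says that these events "should be recorded during the entire course of the study from time of enrollment through end of 180 Day Follow-up visit". That row carries an X at the procedure, discharge, 30-day, 180-day and 365-day columns. The synopsis schedule also marks the row in its combined 180- and 365-day column.

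Section 8 collects device-related events from enrollment "through study completion (withdrawal for any reason or completion of 365-day follow-up visit". Section 8.3 reads: "All device related adverse events observed from the time of enrollment throughout the duration of the study must be reported on the eCRF". Sections 2.3 and 7.6.4 both put the end of a subject's participation at 365 days.

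**Visit descriptions.** Sections 7.6.2 (30 days) and 7.6.3 (180 days) list, among the contents of a typical visit, "review of concomitant medications and any device related adverse events". Section 7.6.4 (365 days) has no such list. It says: "If a clinic visit is not standard of care, follow-up information for this visit will be collected via telephone".

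**Endpoints and analysis.** Section 3.2.2 includes "Incidence of Radial Artery Occlusion Complications at any time". In Section 13.2.1, "duration in study will be based on last study contact date which is the latest date of all follow-up visits". Section 13.5 has missing data counted and only observed cases used, without saying whether adverse event recording that has stopped is missing data.

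**365-day window.** It is ±30 days in the synopsis schedule and in Table 2, and ±60 days in the heading of Section 7.6.4.

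**The concern.** Site staff commonly work from the schedule table and its footnotes. Here the footnote tells them to stop recording at the 180-day visit, and the section describing the 365-day contact does not tell them to ask about adverse events. Section 8 makes device-related adverse event reporting the means of monitoring complications, so a site that stops at 180 days closes the main channel for anything later. Section 1.2 says that no clinical studies of this device have been published, so late device-related events are part of what the registry could contribute.

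There is also a possible analysis consequence. If a late-event rate or a Kaplan-Meier summary used time to last contact, the time after recording stopped would enter as event-free. This is conditional: the plan names no adverse event endpoint as time-to-event.

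The window conflict is a separate and smaller matter. It decides which 365-day visits are protocol deviations (Section 13.8) and how long follow-up may run. It does not change the visit to which data are assigned, because Section 13.2.2 uses the visit label in the eCRF.

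**Working it through.** The plan gives no figure of its own on this point, so the check is a comparison of texts followed by day arithmetic.

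**1. End of device-related adverse event recording, by source**

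| Source | End of recording |
|---|---|
| Table 2 footnote, closing words | 180-day visit |
| Table 2 footnote, opening words | whole study, i.e. 365 days by Sections 2.3 and 7.6.4 |
| Table 2 grid, same row | 365-day visit |
| Synopsis schedule | 180- and 365-day visits (combined column) |
| Section 8 | withdrawal or the 365-day visit |
| Section 8.3 | end of study (no day named) |

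Only the closing words of the footnote point to 180 days.

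**2. Follow-up without recording at a site that obeys the footnote**

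Inputs: 180-day visit on days 150 to 210 (±30, Section 7.6.3); final visit on days 335 to 395 (±30) or 305 to 425 (±60). Days are counted as exact date differences, as in Section 13.2.1. The unrecorded share is (final day − 180-day visit day) / final day.

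- Nominal: (365 − 180)/365 = 185/365 = 50.7%.
- ±30 window, smallest: (335 − 210)/335 = 125/335 = 37.3%. Largest: (395 − 150)/395 = 245/395 = 62.0%.
- ±60 window, smallest: (305 − 210)/305 = 95/305 = 31.1%. Largest: (425 − 150)/425 = 275/425 = 64.7%.

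**3. Share of one-year events that would be missed**

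The documents give no late-event rate, so this is a range by assumption. Let a fraction f of one-year events occur by day 30 and let the rest spread evenly over days 30 to 365. The share falling after day 180 is (1 − f) × 185/335.

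| f | Share missed |
|---|---|
| 1 | 0% |
| 0.9 | 0.1 × 0.552 = 5.5% |
| 0.5 | 0.5 × 0.552 = 27.6% |
| 30/365 (constant hazard) | (335/365) × (185/335) = 50.7% |

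**4. Effect on a zero-event statement (illustration)**

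Section 2.2 states: "Each study site will be limited to 30% of total patient population". Suppose one site enrolls 30 of 100 subjects and follows the footnote, all subjects are followed to the final contact, and no late event is recorded. Late events were then ascertained in 70 subjects. With zero events, the upper limit of the two-sided 95% Clopper-Pearson interval is 1 − 0.025^(1/n).

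- n = 100: 3.6%.
- n = 70: 5.1%.
- A site with 10 of the 100 subjects instead, n = 90: 4.0%.

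Using 100 as the denominator makes the upper limit look tighter than the data support.

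**5. Window conflict**

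±30 days covers days 335 to 395, and ±60 covers days 305 to 425. A visit on days 305 to 334 or 396 to 425 is therefore in window under Section 7.6.4 and a deviation under Table 2 and the synopsis.

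**The case against.** Both contradictions are plain in the current text, so the case on the other side concerns their weight.

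- *The rest of the protocol points one way, and the footnote is one clause.* True, and it makes the correction easy. It does not tell a site which text governs. On-site monitoring checks adherence to the protocol, but a monitor faces the same conflict. The Section 8 provision on events learned of after study exit does not cover days 180 to 365, when the subject is still in the study.
- *Sections 7.6.2 and 7.6.3 only describe what a typical visit may include, so the silence of 7.6.4 means little.* Partly right: the duty to report comes from Section 8 and Table 2. Still, adverse event review is named at the two earlier visits and not at the one contact that may be by telephone.
- *The analysis consequence is hypothetical.* This stands as a limit on the point. No late-event rate or adverse event time-to-event analysis is specified, so the proposed analysis sentence applies only if such a summary is produced.
- *The zero-event example uses the largest permitted site.* Also fair. With a 10-subject site the limits are 3.6% against 4.0%, a much smaller gap.
- *Section 7.6 schedules visits on a 30-day calendar, so exact days are not established.* Section 13.2.1 defines study day as a date difference, which is the basis used here. The window conflict exists under either reading.

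**Conclusion.** The concern holds. The footnote is wrong as written, because it contradicts itself, its own table row, Section 8 and Section 8.3. At a site that follows it, nominally 50.7% of follow-up has no device-related adverse event recording (37% to 62% across the ±30-day windows, 31% to 65% if ±60 applies). The proportion of events lost rests wholly on assumed timing: none if all occur by day 30, about half under a constant hazard. How many sites would follow the footnote is also unknown.

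The effect is confined to device-related event summaries after day 180 and the complications counted at any time. The 30-day primary safety evaluation, procedural and technical success, and the by-site analysis of the primary evaluations (Section 13.4) are untouched. The ±30 and ±60 conflict is also real, and affects deviation counts and permitted follow-up length only. This should be corrected, but it does not threaten the primary results.

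**What to change.** 1. Change the Table 2 footnote so that recording runs through the 365-day visit, in line with the grid, Section 8 and Section 8.3.
2. In Section 7.6.4, name review of device-related adverse events for both telephone and clinic contacts.
3. Add one sentence to Section 13: for any subject whose adverse event recording stopped at 180 days, follow-up time in any late-event rate or Kaplan-Meier summary ends on the last date adverse events were ascertained, not at last contact. Report the number of subjects affected.
4. Reconcile the 365-day window in the synopsis, Table 2 and Section 7.6.4 to a single value. The choice is the sponsor's.

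The cost is a footnote and text correction, one analysis sentence and a memo to sites. No visit is added, since the question is asked at the 365-day contact already planned.

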7.3 Device Set-up and Preparation

Please refer to the IFU for guidance.

7.4 Blood Tests

Blood samples will be collected and analyzed per each site standard of care. Specific blood tests are not required per protocol; examples of typical tests are listed, but only need to be reported if collected per standard of care.

7.5 Concomitant Medical Therapy

Subjects enrolled in this study should be medicated according to investigator's standard of care prior to, during, and after the procedure.

Intraoperative medications and any anticoagulant / antiplatelet medications should be recorded on the appropriate eCRF. Other concomitant medications will not be collected for this study.

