A study by Kis and colleagues, comparing the feasibility of transradial vs transfemoral access for hepatic radioembolization, demonstrated 100% technical success in both radial and femoral cohorts, totaling 64 procedures in 50 patients. Direct savings in cost and time were noted in the radial group; approximately \$100 and 1-hour decrease post procedure stay was observed on a per procedure basis. Despite a caveat noted in this study surrounded the technical challenges associated with radial access which led to longer fluoroscopy time and greater radiation doses, the authors recommended radial access as the primary choice in selected patients, such as those with low platelet count and/or morbid obesity. (Kis, Mills, & Hoffe, 2016) The association between increased radiation exposure and fluoroscopy time with radial access was challenged in a later study, in which 124 intraarterial procedures were performed on 55 liver cancer patients, which demonstrated

significantly less radiation exposure to operators using radial artery access, and similar contrast agent volume and patient radiation exposure between groups. This randomized, prospective study was primarily conducted in order to assess patient access preference for intraarterial liver cancer therapies; of 36 patients who experienced at least one radial and one femoral access procedure, 81% preferred TRA compared to 19% who preferred TFA. (Yamada, et al., 2018)

A recent paper from an Italian University hospital from a study of 60 pts treated with TACE for HCC reported 0% of cross-over rate from trans-femoral access (TFA) to trans-radial access (TRA). A positive association between operator experience and time spent for fluoroscopy, puncture, procedure and total examination was noted. A negative relationship between TRA and contrast volumes and radiation exposure were also reported. A higher percentage of pts treated with TFA reported post-procedural complains at the puncture site and limitations in performing basic activities. The operator learning curve was estimated to be low, with an estimated threshold of 20 procedures. (Iezzi, et al., 2019)

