The largest study involving safety and feasibility of transradial access for non-coronary interventions includes both UFE and hepatic artery embolization among other visceral interventions. In this single center study, 936 patients undergoing 1,512 consecutive TRA procedures were retrospectively analyzed. Of these procedures, UFE accounted for 116, and TACE, Y90 mapping and Y90 infusion accounted for 485, 391 and 293 procedures, respectively. Combined analysis indicated a technical success rate of 98.2%. Major complications, including one pseudoaneurysm and one seizure, were reported at 0.13%, and minor complications, including hematomas, RAO, RAS and arm pain, were observed in 2.38% of cases. Twenty-seven cases, representing 1.8%, required crossover to transfemoral access. The favorability of these results towards radial access led authors to pronounce TRA as a promising alternate primary access site in a variety of peripheral vascular interventions. (Posham, et al., 2016)

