2.1 Study Design

This is a prospective, multi-center, non-randomized registry to record the real-world safety and efficacy of the HydroPearl microspheres for arteriovenous malformations and hypervasculat tumors including uterine fibroids, and for embolization prostatic arteries for symptomatic benign prostatic hyperplasia (BPH).

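### The plan does not provide for recording later treatment of the embolized organ or target-disease drugs, so 180- and 365-day HydroPearl outcomes cannot be separated from what was done afterwards

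*Combined protocol and SAP*

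**What the plan says.** **Purpose.** Section 2.1 describes a "registry to record the real-world safety and efficacy of the HydroPearl microspheres". Section 3.1 gives a narrower objective: technical and procedural success and complication rates.

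**Late outcomes.** Section 3.2.2 lists, by procedure type, mRECIST tumor response, IPSS, UFS-QoL, EQ-5D and other measures. Table 2 (section 7.2) schedules the questionnaires at 180 and 365 days, and target-organ imaging at the same times if available.

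**Drugs.** Section 7.5 says: "Intraoperative medications and any anticoagulant / antiplatelet medications should be recorded on the appropriate eCRF". The next sentence reads: "Other concomitant medications will not be collected for this study". The medication row in Table 2 is ticked at baseline, procedure, discharge and 30 days, and is blank at 180 and 365 days. Section 7.6.3 nevertheless names a review of concomitant medications as something a typical 180-day visit may include.

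**Later procedures.** Section 7.7 names demographics, eligibility and procedure data, then "specific concomitant medications as well as complications and/or device related adverse events will be collected on the eCRFs provided by the Sponsor". Section 8 limits adverse events to those at least possibly related to a device of the manufacturer. Section 3.2.1 counts complications that need surgical or endovascular intervention within 30 days. No section mentions further treatment of the embolized organ as a data item.

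**Analysis.** Late values are analyzed by the visit entered in the eCRF (13.2.2), on observed cases only (13.5), descriptively and without hypothesis tests (13.7). No rule covers values obtained after further treatment.

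**The concern.** A tumor response or symptom score at 180 or 365 days reflects the index embolization plus everything done to that organ since. If the later treatment is not recorded, a subject in whom the index procedure failed, who was treated again and then improved, is indistinguishable from a lasting success. The same holds for a change in drugs directed at the target disease. What is at stake is the meaning of the late summaries. They would be presented as results of HydroPearl, and no method of analysis could later separate the two sources of effect, because neither the event nor its date would be in the database.

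**Working it through.** The plan has no figure on this point. Its one calculation (13.1) concerns complications and reproduces: 1 − 0.984^100 = 0.8007, in line with the stated probability above 80%. It has no bearing here. The check is therefore a reading of the sections together, followed by an illustration of size.

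1. **Could a later event reach the database under the plan as written?**
   - Repeat embolization, surgery or ablation for progression, regrowth or returning symptoms: not a device-related event (section 8), not a medication (7.5), not an item in the evaluation lists (3.2.1, 3.2.2) or Table 2. No route is specified.
   - A target-disease drug started, stopped or changed: excluded expressly by 7.5, at baseline as well as later.
   - An intervention for a device-related event: there is a route, because such events are reported and followed through study completion (sections 8 and 8.3). The footnote to Table 2 stops at 180 days, but that is still well beyond day 30.

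2. **What happens to the late value?** Three hypothetical subjects show it.
   - A liver subject progresses, is embolized again at day 100 and responds at day 180. Under 13.2.2 and 13.5 the 180-day response is tabulated as CR or PR. Late response is overstated.
   - A PAE subject starts a drug for the same symptoms at day 120. The improved IPSS is tabulated at day 180. Improvement is overstated.
   - A PAE subject does well and stops such a drug. Any rise in IPSS from stopping is tabulated too. Improvement is understated.

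3. **Illustration of size (assumptions, not figures from the documents).** Let f be the fraction of a subgroup who are index failures and are re-treated, and r the share of those who then count as responders. The reported response rate rises by f × r.

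| f | r = 50% | r = 80% |
|---|---|---|
| 5% | 2.5 points | 4 points |
| 10% | 5 points | 8 points |
| 20% | 10 points | 16 points |

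In an assumed subgroup of 20, one re-treated failure counted as a responder adds 1/20 = 5 points. For scale, the 95% half-width at an assumed response of 70% with 20 subjects is 1.96 × √(0.7 × 0.3/20) = 0.201, or about 20 points. The shift may thus be smaller than sampling error, but the confidence interval does not include it.

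**The case against.** The case on the other side is substantial.

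- **The procedure part rests on silence.** Nothing says that re-treatment will not be recorded, and the eCRF is not among the documents. Section 7.7 cannot be a complete list, since it omits the questionnaires and imaging that Table 2 schedules. This stands: the supportable statement is that the protocol does not provide for recording later treatment. The drug part is explicit.
- **Some later interventions and drugs may be captured.** Device-related events are followed past day 30, so it would be wrong to infer that only interventions within 30 days are seen. The 180-day visit text also allows for a medication review, but it is permissive and conflicts with 7.5 and Table 2. The gap that remains is target-organ treatment unrelated to the device, and target-disease drugs.
- **Reach.** A reader might infer that the main results are compromised, especially as the synopsis speaks of primary endpoint data at 180 and 365 days. The primary evaluations defined in 3.2.1 are procedural or end at 30 days, so they are not affected. Late imaging is optional and the 365-day contact may be by telephone, so late tumor response may be sparse. Pain VAS and Qmax have no row in Table 2, so late results for them are only inferred.
- **Frequency.** A reader might take the background as showing that re-treatment is common: "124 intraarterial procedures were performed on 55 liver cancer patients" gives 124/55 = 2.25 per patient, and "936 patients undergoing 1,512 consecutive TRA procedures were retrospectively analyzed" gives 1,512/936 = 1.62. Neither measures re-treatment. In the first study, 36 patients had both a radial and a femoral procedure. The second includes 391 mapping procedures; without them it is 1,121/936 = 1.20. The first is liver-only and the second mostly liver, and neither gives a re-treatment figure for PAE, UFE or AVM.
- **Direction.** A uniform upward bias is tempting to infer but not established, as the third subject above shows.
- **Legitimacy of the summary.** Reporting outcomes regardless of later care is a valid real-world summary. That holds if the reader is told how much later care there was. The plan gives no means of saying so.

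**Conclusion.** The concern holds within limits. The protocol expressly excludes target-disease drugs and does not provide for recording later target-organ treatment unrelated to the device. The additional 180- and 365-day evaluations (IPSS, UFS-QoL, EQ-5D, and tumor response where imaged) would therefore be reported as HydroPearl results whatever was done afterwards, with the affected values unidentifiable. Re-treated failures would tend to inflate late response; the net effect of drug changes is unknown. The size cannot be derived from the documents: 5 points per re-treated responder in a subgroup of 20, and 2.5 to 16 points over the grid above, are illustrations resting on assumed subgroup size, re-treatment fraction and subsequent response. The affected evaluations are secondary in rank and descriptive, so this is an improvement the sponsor should make, not a flaw in the primary evaluations. It has to be made prospectively.

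**What to change.** **Data.** Add one dated eCRF item at the 30-, 180- and 365-day contacts, by telephone where that is how the contact is made. It should ask whether, since the last contact, the embolized organ has had any further treatment (repeat embolization, surgery, ablation), and whether any drug for the target disease has been started, stopped or changed, with type and date. Record target-disease drugs at baseline. Amend 7.5 and the Table 2 medication row to match, and reconcile both with the medication-review text in 7.6.3.

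**Analysis.** In 3.2.2 and 13.2, add the re-treatment rate as a reported outcome. Present late response and symptom scores twice: for all subjects regardless of later treatment, and with values after re-treatment counted as non-response or shown separately.

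Recording analgesics with each pain score, and a rule for assigning late access complications when there has been a further radial puncture, are optional refinements.

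**Cost.** Slightly more data entry: an item with a few parts at three existing contacts, plus baseline drugs. No added visit, no change in care or sample size. The late results may look less favorable.
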